### 10.1 Initial Reporting by the Investigator

SAEs occurring during a subject’s participation in the trial or experiment must be reported within 24 hours to the Sponsor’s GPE Department and to the CRA. Every SAE must be reported, even if the Investigator considers that it is not related to the vaccine. The Investigator (licensed physician [M.D. or D.O.]) must validate the information entered on the AE CRF by completing the investigator validation form.

The Investigator must indicate on the AE CRF that the event was serious and must complete the relevant SAE section of this form as well as the appropriate Death/Safety Complementary Information CRFs. An e-mail alert will automatically be sent by the EDC system to the GPE mailbox, the CRA and the CTL with relevant SAE information details.

If the EDC system is unavailable, the site must notify the Sponsor using the paper version of the CRB, as described in the operating guidelines:

The Investigator must complete the paper copies of the AE CRF and of the appropriate Death/Safety Complementary Information CRFs and send them to the Sponsor by one of the following means:

- By fax, to the following number: [REDACTED]
- In PDF format to the following e-mail address, using a method of transmission that includes password protection: [REDACTED]
- By express mail, to the following address:

Global PharmacoVigilance, Sanofi Pasteur  
[name]  
[name]

When the EDC system becomes available, the Investigator must transcribe the information from the paper forms into the EDC system.

If there is need for urgent consultation, the Investigator is to contact the RMO. If the RMO cannot be reached, the Investigator may contact the Call Center as described in [Section 5.3](#).

## **10.2 Follow-up Reporting by the Investigator**

The AE CRF completed initially must be updated within 24 hours after the Investigator has become aware of any new relevant information concerning the SAE (e.g., outcome, precise description of medical history, results of the investigation). All relevant information must be included directly in the AE CRF and the appropriate Death/Safety Complementary Information CRFs. An e-mail alert will be sent automatically to the GPE Department and to the CRA. Copies of documents (e.g., medical records, discharge summary, autopsy) may be requested by the GPE Department.

The anonymity of the subject must always be respected when forwarding this information.

## **10.3 Reporting of SAEs Occurring After a Subject Has Completed the Study**

Any SAE that occurs after a subject has completed the study but that is likely to be related to the investigational products or to the experiment must also be reported as soon as possible. In such a case, the reporting procedure to be followed is identical to that described in [Section 10.1](#).

## **10.4 Assessment of Causality**

The causal relationship between the SAE and the product administered will be evaluated by the Investigator as described in [Section 9.2.2.3.5](#).

Following this, the Sponsor's Pharmacovigilance (PV) Global Safety Expert (GSE) will also assess the causal relationship to the product, based on the available information and current medical knowledge.

The causal relationship to study procedures will be also assessed in the CRB.

The decision to modify or discontinue the trial may be made after mutual agreement between the Sponsor and the Investigator(s).

## 10.5 Reporting SAEs to Health Authorities and IECs / IRBs

The Sponsor will inform the relevant health authorities of any reportable SAEs according to the local regulatory requirements. Reporting to the health authorities will be according to the Sponsor's standard operating procedures.

The Sponsor's RMO ( [REDACTED], [REDACTED] ) will notify the Investigators in writing of the occurrence of any reportable SAEs. The Investigators / Sponsor will be responsible for informing the IECs or IRBs that reviewed the trial protocol.

## 11 Data Collection and Management

### 11.1 Data Collection and CRB Completion

Individual diary cards, specifically designed for this trial by the Sponsor and provided to the study sites, will be given to study participants for the recording of daily safety information as described in [Section 9.2.2.3](#). These diary cards will include prelisted terms and intensity scales (see [Table 9.1](#) and [Table 9.2](#)) as well as areas for free text to capture additional safety information or other relevant details. Subjects will also be provided with rulers for measuring the size of injection site reactions, and with standard digital thermometers for measuring daily temperatures. To ensure consistency of reporting, the study sites will instruct subjects on how to correctly use these tools.

The D180 follow-up will be done by interviewing subjects over the telephone using a questionnaire to capture SAEs and AESIs, if applicable. A memory aid will be provided to the subjects at the preceding trial visit to help them record information on events occurring between this visit and the D180 follow-up.

Relevant information will be transcribed into the AE CRF. Any SAEs captured during this 6-month follow-up period will be reported and followed-up as per the normal process for reporting SAEs.

At specified intervals, the Investigator or an authorized designee will interview the subjects to collect the information recorded in the diary card, and will attempt to clarify anything that is incomplete or unclear. All clinical trial information gathered by the study site will be reported electronically by the Investigator or authorized designee using a web-based CRB. (Any information that was not documented in the diary card will first be captured in the source document and then reported electronically). The CRB has been designed specifically for this trial under the responsibility of the Sponsor, using a validated Electronic Records / Electronic Signature-compliant platform (21 CFR Part 11).

To ensure the correct and consistent completion of the CRBs, the Sponsor or authorized representative will provide all necessary tools, instructions, and training to all site staff involved in data entry prior to study start. Additional instructional documents such as training manuals and completion instructions will be provided to assist with data entry during the course of the trial.

Upon completion of training, each user requiring access to the EDC system will be issued a unique username and password. In the event of a change in trial personnel, each newly assigned

individual will receive a unique username and password; the username and password of a previous user may not be reissued. If any trial personnel leave the study, the Investigator is responsible for informing the Sponsor immediately so that their access is deactivated. An audit trail will be initiated in the EDC system at the time of the first data entry in order to track all modifications and to ensure database integrity.

The Investigator is responsible for the timeliness, completeness, and accuracy of the information in the CRBs; must provide explanations for all missing information; and must sign the CRB using an e-signature.

## **11.2 Data Management**

### ***Management of SAE Data***

During the study, SAE data (reported on the AE, Death, and Safety Complementary Information CRFs) will be integrated into the Sponsor's centralized GPE database upon receipt of these forms and after a duplicate check. Each case will be assigned a case identification number. Each case will be assessed by the case management platform or its delegate before being reported to the relevant authorities as necessary. The assessment of related cases will be done in collaboration with the PV GSE and the RMO. Follow-up information concerning a completed case will be entered into the GPE database, and a new version of the case will be created.

The information from the GPE database cases will be reconciled with that in the clinical database.

### ***Management of Clinical and Laboratory Data***

Clinical data, defined as all data reported in the CRB, and laboratory data will be handled by the Sponsor's Clinical Data Management (CDM) platform or authorized representative.

During the trial, clinical data reported in the CRBs will be integrated into the clinical database under the responsibility of the Sanofi Pasteur CDM platform. Data monitoring at the sites and quality control in the form of computerized logic and / or consistency checks will be systematically applied in order to detect errors or omissions. In addition, data reviews may be performed several times by the Sponsor's staff in the course of the trial. Any questions pertaining to the reported clinical data will be submitted to the investigator for resolution using the EDC system. Each step of this process will be monitored through the implementation of individual passwords to maintain appropriate database access and to ensure database integrity.

The validation of the immunogenicity data will be performed at the laboratory level following the laboratory's procedures. Information from the laboratory will be checked for consistency before integration into the clinical Datawarehouse.

After integration of all corrections in the complete set of data, and after the SAE information available from CDM and the GPE Department has been reconciled, the database will be released for statistical analysis.

### 11.3 Data Review

A blind review of the data is anticipated through the data review process led by Data Management before database lock.

## 12 Statistical Methods and Determination of Sample Size

### 12.1 Statistical Methods

Clinical database data will be analyzed under the responsibility of the Biostatistics Platform of the Sponsor, US, with the SAS software, at least version 9.4 (SAS Institute, Cary, North Carolina, USA).

A statistical analysis plan (SAP) will be written and peer reviewed before any analyses. In accordance with the protocol, the SAP will describe all analyses to be performed by the Sponsor and all the conventions to be taken.

For the purposes of the statistical methods section, the 4 virus strains in the QIV-HD trial groups and the TIV-HD trial groups will be labeled as follows:

- A/Michigan/45/2015 (H1N1) strain                    A1
- A/Hong Kong/4801/2014 (H3N2) strain            A2
- B/Brisbane/60/2008 strain                            B1
- B/Phuket/3073/2013 strain                           B2

#### 12.1.1 Hypotheses and Statistical Methods for Primary Objective

##### 12.1.1.1 Immunogenicity

###### 12.1.1.1.1 Hypotheses

The immunogenicity of QIV-HD will be compared to that of TIV-HD1 and / or TIV-HD2. For each A strain, the comparison will be made with the pooled TIV-HD groups. For each B strain, the comparison will be made with the TIV-HD group containing the corresponding B strain.

For each strain, a non-inferiority approach will be used to compare the post-vaccination GMTs and the seroconversion rates between the groups using a 1-sided Type I error rate of 0.025 with the given individual hypothesis:

$$H_0^s : \frac{GMT_{QIV-HD}^s}{GMT_{TIV-HD}^s} \leq \frac{1}{1.5}$$

- $\Leftrightarrow \log_{10}(GMT_{QIV-HD}^s) - \log_{10}(GMT_{TIV-HD}^s) \leq -\log_{10}(1.5)$

$$H_A^s : \frac{GMT_{QIV-HD}^s}{GMT_{TIV-HD}^s} > \frac{1}{1.5}$$

$$\Leftrightarrow \log_{10}(GMT_{QIV-HD}^s) - \log_{10}(GMT_{TIV-HD}^s) > -\log_{10}(1.5)$$

- $H_0^s : \pi_{QIV-HD}^s - \pi_{TIV-HD}^s \leq -0.1$
- $H_A^s : \pi_{QIV-HD}^s - \pi_{TIV-HD}^s > -0.1$

with:

- s: strain in {A1, A2, B1 and B2}
- If s in {A1 and A2}, TIV-HD represents the pooled TIV-HD1 and TIV-HD2 groups
- If s = B1, TIV-HD represents the TIV-HD1 group
- If s = B2, TIV-HD represents the TIV-HD2 group
- $\pi$ : The seroconversion rate

#### 12.1.1.1.2 Statistical Methods

Assuming that  $\log_{10}$  transformation of the data follows a normal distribution, the  $\log_{10}$  (data) will be used for the statistical analysis, then antilog transformations will be applied to the results of calculations, in order to provide the results in terms of geometric means (GMs).

The statistical methodology will be based on the use of the 2-sided 95% CI of the ratio of post-vaccination GMTs and difference in seroconversion rates between QIV-HD and TIV-HD groups. The 95% CIs will be calculated by normal approximation of log-transformed titers for GMTs and by the Newcombe-Wilson score method without continuity correction for seroconversion rates. The margins used for non-inferiority hypothesis testing are 1.5 for GMTs and 10% for seroconversion rates based on Food and Drug Administration (FDA) guidelines for licensure of seasonal influenza vaccine (11).

The non-inferiority objective will be achieved only if it is demonstrated for 4 strains and for both GMTs and seroconversion rates. Analyses will be performed for both the Full Analysis Set (FAS) and the Per-protocol Analysis Set (PPAS), but the conclusion will be made from PPAS results.

A sensitivity analysis will be performed with adjustment on the pre-vaccination HAI titers.

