## **5.1.4 Visit Procedures**

### ***Visit 1 (D0): Inclusion, Randomization, Blood Sample, and Vaccination***

- 1) Explain the trial to the subject, answer any of his / her questions and ensure that he / she has been informed of all aspects of the trial that are relevant to his / her decision and obtain a written informed consent signed by the subject. If the subject is illiterate, an independent witness/legal representative is required to sign the consent form.

The Investigator / delegate will also sign and date the ICF. The Investigator / delegate will then retain one original and give the copy to the subject.

- 2) Check all inclusion and exclusion criteria (see [Section 5.2.4](#) and [Section 5.2.5](#), respectively) through physical examination and medical interview. If the subject is not eligible, only the specific form entitled “Recruitment log” will state the subject identification, no CRB will be completed.
- 3) Collect relevant demographic information (e.g., date of birth and gender).
- 4) Obtain information about history of influenza vaccination in the previous year.
- 5) Collect significant medical history and record any planned hospitalization during the trial in the CRB and other source documents.
- 6) Collect reportable concomitant medications (see [Section 6.7](#)).

- 7) Perform and document a targeted physical examination per standard site-specific immunization practices and record oral temperaturea in the medical chart.
- 8) Call the IRT to assign to the subject a 12-digit subject number and allocate a medication number (see [Section 6.5](#)). At this time, some subjects will be assigned to the Expanded Immunogenicity Subset.
- 9) Draw an approximately 10 mL blood sample (This blood sample should be performed before vaccination). Process the blood sample as specified in the “Management of Samples” section (see [Section 7](#)). Note: If the subject withdraws consent before blood sampling (before any invasive procedure has been performed), do not vaccinate the subject. The subject should be terminated from the study. **Note:** If the attempt(s) to collect blood is (are) unsuccessful (3 attempts), then the subject is still to be included in the study and vaccinated.
- 10) Administer the corresponding vaccine to the subject in the region of the upper arm muscle (the vaccine must be administered on the side opposite to that of the blood sampling).

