#### *Superiority of QIV-HD to TIV-HD1 or TIV-HD2*

The statistical methodology will be based on the use of the 2-sided 95% CI of the ratio of post-vaccination GMTs and difference in seroconversion rates between the QIV-HD group and TIV-HD group. The 95% CIs will be calculated using normal approximation of log-transformed titers for GMTs and using the Newcombe-Wilson score method without continuity correction for seroconversion rates. For each strain, the 2-sided 95% CI should lie above 1.5 for GMTs and above 10% for seroconversion rates.

The superiority objective will be achieved if the superiority is demonstrated for both B strains and for both GMTs and seroconversion rates. Analyses will be performed for both FAS and PPAS but the conclusion will be made from FAS results.

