##### 12.2.1 Full Analysis Sets

The FAS is defined as the subset of randomized subjects who received at least 1 dose of a trial vaccine and had a post-vaccination blood sample HAI result for at least 1 strain. Subjects will be analyzed according to the vaccine group to which they were randomized.

For the assessment of the immune response by virus SN method, the analysis will be performed on the subjects from the FAS randomized into the Expanded Immunogenicity Subset with at least one post-vaccination SN assay result for at least 1 strain.

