### 12.3.2 Immunogenicity

In order to appropriately manage replicate values for analysis purposes, the individual GM of all values will be computed for each blood sample after managing extreme values as described. The computed value is then considered the titer for that particular blood sample.

- If a titer is  $< \text{LLOQ}$ , then the computed value,  $\text{LLOQ}/2$ , will be used.
- If a titer is  $\geq \text{LLOQ}$  and  $< \text{ULOQ}$  (or  $\leq \text{ULOQ}$ ), then the titer itself will be used.
- If a titer is  $\geq \text{ULOQ}$  (or  $> \text{ULOQ}$ ), then computed value,  $\text{ULOQ}$ , will be used.

Any other replacement to be applied to specific endpoints will be described in the SAP.

No test or search for outliers will be performed.

No replacement will be done for missing values. Based on the previous TIV-HD and QIV-SD trials in this population, the amount of missing immunogenicity data is expected to be  $\leq 5\%$  in this trial. Usually in vaccine trials, it seems generally reasonable to assume missing immunogenicity data are missing completely at random (MCAR) (13). Indeed, it is highly unexpected that the dropout (or any other reason for missing data) could be linked to the immune response of the subject. Therefore, confirming the results of the PPAS for the primary analysis with the FAS would be satisfactory in terms of sensitivity analysis.

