## 12.5 Determination of Sample Size and Power Calculation

A total of 2616 adults aged 65 years and older will be enrolled. A sample size of 2616 is determined based on an overall power of 90% for demonstrating non-inferiority for both the HAI GMTs and seroconversion rates comparing QIV-HD vs TIV-HD1 and / or TIV-HD2 for all 4

virus strains. The non-inferiority margins are defined as 1.5 for GMTs and 10% for seroconversion rates.

Assumptions for the above calculations are:

- The expected seroconversion rates for the 4 strains: 45% for A1 strain, 70% for A2 strain, and 40% for both B strains.
- Assumed standard deviations for HAI GMTs are 0.63 for both A strains and 0.55 for both B strains.
- An 8% attrition rate which provides approximately 2407 evaluable adults for immunogenicity analysis.

Based on current sample size, there is 55.4% power to detect the superiority of each B strain comparing QIV-HD groups versus either the TIV-HD1 or TIV-HD2 group in the secondary objective. It is based on an assumption of expected GMT ratio of 1.8 with a standard deviation of 0.55, seroconversion rate of 8% in the group without the B strain and 22% increase in the group with the B strain, and a 5% attrition rate in FAS.

A subset of 300 subjects with 100 subjects from each group will be randomly selected for SN testing.

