## 5 Statistical Methods and Determination of Sample Size

See Section 5 of the SAP core body for the same analysis plan. Subsections are deleted if they are not applicable for immunogenicity analyses by ELLA.

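### The superiority GMT decision ignores the D0 titer, and the 55.4% power stated for each B strain is really the power for both strains together (about 74.6% per strain)

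*Protocol*

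**What the plan says.** Protocol Section 5.1.1 schedules a D0 blood sample for HAI testing in every subject. Adjustment for that baseline appears in one place, under the primary non-inferiority objective (Section 12.1.1.1.2, repeated in the synopsis): "A sensitivity analysis will be performed with adjustment on the pre-vaccination HAI titers".

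For superiority, Section 12.1.2.1.2 states: "The 95% CIs will be calculated using normal approximation of log-transformed titers for GMTs". No baseline covariate is named there, even for sensitivity. The lower limit must exceed 1.5 for the GMT ratio and 10 points for seroconversion, and the conclusion comes from the FAS. The success rule is: "The superiority objective will be achieved if the superiority is demonstrated for both B strains and for both GMTs and seroconversion rates".

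On power, Section 12.5 and the synopsis say "there is 55.4% power to detect the superiority of each B strain comparing QIV-HD groups versus either the TIV-HD1 or TIV-HD2 group".

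Three other provisions bear on any use of the D0 titer:

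- Section 5.1.4: if three attempts at the D0 draw fail, "then the subject is still to be included in the study and vaccinated".
- Section 12.2.1: FAS members need to have been vaccinated and to have "had a post-vaccination blood sample HAI result for at least 1 strain"; no D0 result is required.
- Section 12.3.2: "No replacement will be done for missing values".

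The SAP supplied is an addendum for one additional assay. Its Section 5 reads: "See Section 5 of the SAP core body for the same analysis plan". That core body is not among the documents.

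**The concern.** There are two linked problems.

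**The label on the power.** Taken at its word, 55.4% is the chance of success for one B strain. A reader who then applies the rule that both strains must succeed would put the objective at 0.554² = 0.307, about 31%. If 55.4% is already the joint figure, the true per-strain chance is much higher and the 31% is wrong.

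**Where the adjustment sits.** The plan adjusts for baseline where precision is not needed (non-inferiority GMT power is nearly 100%) and does not where it is short. Superiority is a hypothesis-tested secondary objective with about a 45% chance of failing even if the assumed ratio of 1.8 is true. The D0 titer is already collected and could narrow the GMT interval without adding subjects.

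**Working it through.** **Inputs.** QIV-HD 1744 and 436 in each TIV-HD group (Section 5.1.1); ratio 1.8, log10 SD 0.55, seroconversion 8% against 30%, 5% FAS attrition (Section 12.5); bounds 1.5 and 10 points, one-sided 0.025 (Section 12.1.2.1.1). Evaluable: 1744 × 0.95 = 1656.8 and 436 × 0.95 = 414.2.

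**Reproducing the stated power.**

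- SE = 0.55 × √(1/1656.8 + 1/414.2) = 0.03021
- Effect beyond the bound = log10(1.8/1.5) = 0.07918
- GMT power per strain = Φ(0.07918/0.03021 − 1.960) = Φ(0.661) = 74.6% (t-based 74.5%)
- Seroconversion power, simulated with the Newcombe interval: above 99.99%
- Both strains, treated as independent: 0.7456² = 55.6% (t-based 55.5%; 413 evaluable per TIV-HD arm gives 55.4%)

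So 55.4% is the joint power. Other per-strain readings do not fit: no attrition gives 76.7% and 8% attrition gives 73.2%. A 1:1 comparison of 414 against 414 gives 54.4%, but that contradicts the 4:1:1 allocation and fits less well.

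**Independence.** The two comparisons share only the QIV-HD arm. With 4:1 allocation that arm contributes one fifth of the variance, since (1/1656.8)/(1/1656.8 + 1/414.2) = 0.2. The correlation between the two test statistics is therefore at most 0.2, and joint power at most about 57.7%.

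**Effect of adjustment.** With a common D0–D28 correlation r on the log scale, the SD becomes 0.55 × √(1 − r²). The documents give no r, so the range is shown:

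| r | per strain | both strains |
|---|---|---|
| 0 | 74.6% | 55.6% |
| 0.1 | 75.0% | 56.2% |
| 0.2 | 76.3% | 58.2% |
| 0.3 | 78.4% | 61.5% |
| 0.4 | 81.6% | 66.6% |
| 0.5 | 85.7% | 73.4% |
| 0.6 | 90.6% | 82.1% |
| 0.7 | 95.6% | 91.5% |

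Joint power of 80% needs r of about 0.58. Without adjustment it needs 622 evaluable per TIV-HD arm, and 622/0.95 × 6 is about 3930 enrolled instead of 2616.

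**Different correlations by arm.** One arm receives the strain and the other does not, so r may differ. In simulation (12,000 replicates for power, 25,000 at a true ratio of 1.5):

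| r in QIV-HD / TIV-HD | joint power, robust SE | type I error, ordinary SE | type I error, robust SE |
|---|---|---|---|
| 0.3 / 0.6 | 74% | 1.6% | 2.6% |
| 0.6 / 0.3 | 62% | 4.2% | 2.6% |

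The unadjusted test also has 2.6%. Ordinary ANCOVA errors are unsafe here because 4:1 allocation gives the larger arm most of the weight in the pooled residual variance.

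**Subjects without D0.** If a share m of the FAS has no D0 titer and is dropped from the model, the variance is multiplied by (1 − r²)/(1 − m). The gain is positive only when r > √m: 0.10, 0.17 and 0.22 for m of 1%, 3% and 5%. These values of m are assumptions.

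**Non-inferiority.** At a true ratio of 1 and 8% attrition, GMT power is 99.9997% for the A strains and 99.992% for the B strains, so adjustment adds nothing material there.

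**The case against.** The unadjusted interval is a valid, prespecified test of the stated hypothesis, with type I error near nominal, and it matches the power calculation. A preference for ANCOVA is about efficiency, and its benefit rests on a correlation found nowhere in the documents. It also has costs: ordinary standard errors can inflate the error rate, and a complete-case model takes the GMT conclusion off the full FAS. The unseen SAP core body may already add such an analysis. As for the power, the secondary objective is itself worded strain by strain and Section 12.1.2.1.2 demands both, so *each* can be read as each and every. On that reading 55.4% is right, and the low power is openly disclosed in a trial sized for its primary objective.

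Much of this stands. The unadjusted analysis is not an error, the gain may be small, and nothing can be said about the core body. But robust errors restore the error rate. The seroconversion criterion already depends on a D0 titer, so the superiority conclusion does not rest on D28 results alone as things are. The charitable reading of *each* is possible, but the sentence also sets QIV-HD against either TIV-HD group, which invites a per-comparison reading, and no per-strain figure is given to correct it.

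**Conclusion.** Both parts hold. The 55.4% is numerically sound but mislabelled: it is the joint power for both B strains, and the per-strain figure is about 74.6%. That follows from the protocol's own inputs. The joint figure assumes independent strains, and the shared arm can raise it only to about 57.7%.

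In the protocol, the superiority GMT decision leaves the D0 titer unused although this is the comparison that lacks power. This is a missed gain in precision and does not threaten validity. Its size depends on an unknown correlation: under 3 points of joint power at r of 0.2 or below, about 6 at 0.3, 18 at 0.5 and 26 at 0.6, less any loss from dropping subjects without D0. The change should be made, with medium confidence, because the size of the benefit and the content of the SAP core body are unknown.

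**What to change.** 1. Before unblinding at the D28 analysis (Section 12.4), specify in Section 12.1.2.1.2, the synopsis and the SAP that the superiority GMT decision uses an ANCOVA of log10 D28 titer on group and log10 D0 titer of the same strain. Use heteroscedasticity-robust standard errors and keep the 1.5 bound. Retain the unadjusted ratio as the sensitivity analysis.
2. State a rule for FAS subjects with no D0 titer. One that fits the no-replacement policy is to fit the model on FAS subjects with both D0 and D28 titers for the strain and report the unadjusted ratio on the full FAS. Say also how these subjects count for seroconversion, whose definition (Section 9.1.1.1) needs a D0 titer.
3. In Section 12.5 and the synopsis, restate the unadjusted power as about 74.6% per B strain and about 55.4% for both.
4. Leave the non-inferiority decision analysis as it is.

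The cost is wording and one standard model, with no new data. The drawbacks are that the headline superiority ratio becomes model-based, a missing-baseline rule is needed, and with a low correlation the gain may be nil.
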